8.7. Analysis of Safety

8.7.1. Extent of Exposure

No diary data were collected on whether a patient used or did not use SD-101-6.0 on a given day. Therefore the number of days on the study will be considered number of days of exposure. It will be summarized using descriptive statistics by overall. Descriptive statistics will also be provided for duration of exposure into categorical summary of <30, >=30 to <90, >=90 to <180, >=180 to <1 year, >=1 year to <2 years, >=2 years.

8.7.2. Adverse Events by Preferred Term and System Organ Class

For the first interim analysis serious AEs will be mapped to system organ class (SOC) and preferred terms (PTs) using the 19.1 version of MedDRA.

If there is a gap between the completion of the study SD-005 and the start of the study SD-006, adverse events starting after the last study day or changing the severity or relationship to treatment within the gap will be counted as medical history for the extension study SD-006. Continuing adverse events will also be captured in medical history for the extension study SD-006. If the severity or relationship to treatment changed on or after the first dose of study medication, then that AE is considered a TEAE after that change.

If an AE started after signing an informed consent/assent but before the first dose of study medication was taken in the study SD-006, then such an AE is non treatment-emergent.

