13.3.1 Definitions

Adverse Event (AE)

Any untoward medical occurrence in a patient, administered a medicinal product and which does not necessarily have to have a causal relationship with this treatment. An adverse event (AE) can therefore be any unfavorable and unintended sign (including an abnormal laboratory finding, for example), symptom, or disease temporally associated with the use of a medicinal product, whether or not considered related to the medicinal product. AEs may include the onset of new illness and the exacerbation of pre-existing conditions.

The routine evolution of the disease condition under treatment according to the protocol will be evaluated as part of the disease symptoms assessments. Changes in the disease condition may not qualify as AEs. However, if there is a clinically relevant worsening of a sign or symptom of the condition under treatment and the outcome fulfills the definition of an AE, it must be reported as directed in the protocol.

Adverse Drug Reaction (ADR)

All events considered to be noxious and unintended responses to a medicinal product related to any dose should be considered adverse drug reactions, with the exception of skin site changes captured during the skin site evaluations (refer to Section 9.3). A lack of efficacy (i.e. worsening EB) should not be considered an ADR. Changes outside of the intended effect (e.g. rash) should be considered ADRs. The phrase "responses to a medicinal product" means that a causal relationship between a medicinal product and an adverse event is at least a reasonable possibility, i.e., the relationship cannot be ruled out.

Serious Adverse Event (SAE)

An adverse event that:

- Results in death
- Is life-threatening (i.e. the patient was at risk of death at the time of the event; it does not refer to an event which hypothetically might have caused death if it was more severe)
- Results in hospitalization or prolongation of existing hospitalization
- Results in persistent or significant disability/incapacity
- Is a congenital anomaly / birth defect
- Is considered to be an important medical event

Based upon medical and scientific judgment, important medical events that may not be immediately life-threatening, or result in death or hospitalization, but may jeopardize the patient or may require intervention to prevent one of the other outcomes listed in the definition above may be considered a serious adverse event.

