6.5.2. Adverse Events

Treatment-emergent adverse events (TEAEs) are any untoward medical occurrence in a patient, administered a medicinal product and which does not necessarily have to have a causal relationship with this treatment. An adverse event (AE) can therefore be any unfavorable and unintended sign (including an abnormal laboratory finding, for example), symptom, or disease temporally associated with the use of a medicinal product, whether or not considered related to the medicinal product. AEs may include the onset of new illness and the exacerbation of pre-existing conditions. Treatment-emergent AEs will be collected after signing the informed consent/assent through the last study visit. If there is a gap between the completion of the Study SD-005 and the start of Study SD-006, adverse events starting after the last study day or changing in severity or relationship to treatment within the gap will be recorded in the medical history for study SD-006. Continuing adverse events will be also captured in medical history for the extension study SD-006.

Medical review will take place to determine if any of AEs could be potentially related to the contamination of the study medication during the manufacturing process. The investigator's

verbatim term of both serious and non-serious AEs will be mapped to system organ class (SOC) and preferred terms (PTs) using the 19.1 version of the Medical Dictionary for Regulatory Activities (MedDRA). Partial dates will be imputed as the following:

1. If year is not missing and is after the year of first application of study drug:
 - a. If Month is missing, then Month will be imputed as January.
 - b. If Day is missing, then Day will be imputed as the first of the month.
2. If year is not missing and is the same as the year of the first application of study drug:
 - a. If Month is missing, then impute the Month as the month of the first application of study drug.
 - b. If Day is missing but Month is on or after the month of first application of study drug, then impute Day as the first day of - the month.
 - c. If the Day and Month are missing then impute Day and Month as the Day and Month of the first study drug application.
3. If year is missing then impute the year as the year of the first study drug application:
 - a. If Month is missing, then impute the Month as the Month of the first study drug application.
 - b. If Day is missing, then impute the Day as the day of the first study drug application.

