8.7.3. Summaries of Adverse Event Incidence Rates for All Patients

The number and percentage of patients who experienced TEAEs will be presented by SOC and by PT within SOC for each treatment group. Treatment-emergent AEs (TEAEs) will be similarly presented by severity (mild, moderate, severe), by relationship to study drug (unrelated, definite, probable, and possible) and by outcome of events. Additionally, the number of TEAEs (as opposed to the number and percentage of patients) will be presented by treatment group.

The number of patients with TEAEs and number of TEAEs will also be presented by the following subgroups of Age (28 days to <2 years, 2 years to <12 years, 12 years to ≤18 years, >18 years). Subgroups for age are defined based at the patient's age at Baseline.

To count the number of patients who experienced each TEAE, a patient experiencing the same TEAE multiple times will only be counted once for the corresponding PT. Similarly, if a patient experiences multiple TEAEs within the same SOC, the patient will be counted only once for that SOC. If a patient experiencing more than one TEAE within different severity or relationship categories within the same SOC/PT, only the worst case (worst severity and related TEAE) will be reported. TEAEs will be sorted alphabetically by SOC and within each SOC the PT will be presented by decreasing order of total frequency.

For TEAE summary by outcome, if a patient experienced more than one TEAE, the worst outcome will be counted under that patient. If a patient experienced more than one outcome within a SOC (or PT), the patient is only counted once under worst outcome in that SOC (or PT).

In addition, all adverse events will be provided by study site and by treatment group, in a listing, which will include the patient identifier, the PT, the reported term, the severity, the seriousness, the action taken, the outcome, the causality, the date onset, date of onset relative to the date of the first study drug administration, date of resolution, date of resolution related to the first study drug administration, and the TEAE duration (resolution date –onset date +1).

Additionally, the incidence and the number of non-serious TEAEs will be presented by treatment group.

Non treatment-emergent AEs, if any, will be listed.

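### SAP 8.7.2 makes a carried-over adverse event treatment-emergent on any change in severity or relationship, so a decrease counts as well as an increase

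*SAP*

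**What the plan says.** SAP 8.7.2 first sends events already present at rollover to medical history. On events in the gap between the studies it says: "adverse events starting after the last study day or changing the severity or relationship to treatment within the gap will be counted as medical history". On those still running it says: "Continuing adverse events will also be captured in medical history for the extension study SD-006". SAP 6.5.2 says the same.

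The next sentence in 8.7.2 brings some of these events back: "If the severity or relationship to treatment changed on or after the first dose of study medication, then that AE is considered a TEAE". The sentence ends by dating the TEAE from the change. It does not say whether the change must be upward.

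The general definition in SAP 6.5.2 adds no such condition: "Treatment-emergent adverse events (TEAEs) are any untoward medical occurrence in a patient, administered a medicinal product", followed by the usual wording for any adverse event. Protocol 13.3.1 states, and SAP 6.5.2 repeats: "AEs may include the onset of new illness and the exacerbation of pre-existing conditions".

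Under SAP 8.7.3, TEAEs are tabulated "by severity (mild, moderate, severe), by relationship to study drug (unrelated, definite, probable, and possible) and by outcome of events". Under SAP 7.1, data are summarised by SD-005 treatment group.

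**The concern.** Adverse events are part of the primary endpoint (Protocol 9.2), and TEAE incidence is a main way of reporting them. A carried-over event should become treatment-emergent because it got worse on SD-101-6.0. A rule triggered by any change also admits events that got better or were judged less related to the drug.

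Such an event would enter the SOC and preferred-term tables as emergent on SD-101-6.0, at its lower severity or relationship category. A serious event continuing from SD-005 that fell a grade could likewise reach the treatment-emergent SAE tables of SAP 8.7.5. In the group that took placebo in SD-005, an event that began on placebo and eased after the switch would count as emergent on active drug. The study has no concurrent control against which a reader could judge the excess.

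**Working it through.** The plan gives no figure to reproduce. The check has three steps.

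**1. Does any other text supply a direction?**
- SAP 6.5.2, TEAE definition: no worsening condition.
- SAP 6.5.2 and 8.7.2, gap rule: the same neutral idea of a change, with no direction.
- Protocol 13.3.1 and SAP 6.5.2, exacerbation sentence: this says what adverse events may include, not when a carried-over event becomes treatment-emergent.
- Protocol 13.3.1, disease under treatment: "if there is a clinically relevant worsening of a sign or symptom of the condition under treatment". This governs whether a change in EB is reported as an adverse event; it does not define a TEAE.
- SAP 8.7.3, worst-case rule: this chooses which category is shown when a patient has several TEAEs in the same SOC or preferred term. It does not remove an event that entered through improvement.

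No text supplies a direction.

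**2. What does the literal rule admit?** The inputs are three severity grades and four relationship categories (SAP 8.7.3; the relationship order unrelated, possible, probable, definite follows Protocol 13.3.2).
- States: 3 × 4 = 12. Before/after pairs: 12 × 12 = 144.
- Pairs with no change: 12. Pairs with a change: 144 − 12 = 132. All 132 create a TEAE as written.
- Pairs in which neither rating rises: 6 severity pairs × 10 relationship pairs = 60. Less the 12 unchanged pairs, this leaves 48 in which something falls and nothing rises.
- Share: 48 / 132 = 36.4%. Pairs in which at least one rating rises: 132 − 48 = 84.

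These are counts of possible transitions, not expected frequencies.

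**3. How many patients might be affected?** The documents give neither the number of events ongoing at rollover nor how often they are re-rated. About 150 patients are planned (SAP 4.4). Assume that a share p carries over an event and that a share q of those patients has only a drop in category. Patients affected = 150 × p × q.
- Low: 150 × 0.05 × 0.25 = 1.875, about 2 patients (1.25%).
- Middle: 150 × 0.10 × 0.50 = 7.5 patients (5%).
- High: 150 × 0.20 × 0.50 = 15 patients (10%).

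Both p and q are assumptions. The proportion of patients with any TEAE would move by no more than this, and by less where an affected patient has another TEAE.

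**The case against.** The strongest reply is that a trained programmer would read a change as a worsening, that the error overstates risk, and that it is harmless in a descriptive study without group comparisons. SAP 8.7.3 also lists every adverse event with severity, causality and onset relative to first dose, so a reader could pick out carried-over events. Part of this stands: no risk is hidden, and the listings help. But incidence tables are programmed from the written rule, and a literal derivation would test for inequality. If worsening is meant, the sentence should say so.

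A second reply is that the route from a medical-history item to a new TEAE record is not shown. Protocol 13.3 has SD-005 events noted in medical history at Visit 1 only, and the documents do not show whether later ratings of those items are captured. This stands as a limit on size: if they are not captured, the rule seldom fires in either direction. Protocol 17.5 requires the patient file to record whether adverse events improved or worsened, so direction should exist at source.

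A reader might also infer more than the documents support:
- *That the rule reaches events starting between consent and first dose.* The next paragraph of SAP 8.7.2 calls these non-treatment-emergent, with no exception for later change.
- *That the protocol admits a pre-existing condition only on exacerbation, so the SAP contradicts it.* The protocol says what adverse events may include. The rule sits badly with that idea but does not contradict a stated limit.
- *That better resolution means more TEAEs.* Resolution is an outcome, tabulated separately. A mild event has no lower grade to fall to, and an event that ends without re-rating triggers nothing.
- *That the severity distribution must move towards mild.* An event may fall only from severe to moderate.

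**Conclusion.** The rule is wrong as written. For events continuing from SD-005 or arising in the gap, a fall in severity grade or a lower causality rating after first dose is enough to create a TEAE. New-onset events are untouched. The bias is towards overcounting, in tables that serve the primary objective.

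That 48 of 132 possible changes are pure decreases follows from the stated categories alone. The range of about 2 to 15 of 150 patients rests wholly on the assumed shares and on re-ratings being recorded. It shows scale and is not an estimate. The case for changing the text rests on the literal reading and the small cost of correction, not on that range.

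**What to change.** In SAP 8.7.2, replace the sentence with:

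> If, on or after the first application of SD-101-6.0 in SD-006, the severity of a continuing or gap event increased, or its relationship moved to a higher category (unrelated < possible < probable < definite), the event is a TEAE from that date. A decrease in severity or relationship alone does not make an event treatment-emergent.

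The relationship clause must cover every upward step. A narrower clause, counting only a move from unrelated into a related category, would retain 66 of the 84 transitions with an increase: 3 rises in severity × 16 relationship pairs = 48, plus 6 severity pairs without a rise × 3 moves out of unrelated = 18. It would lose the other 84 − 66 = 18, such as possible to probable at unchanged severity. A long-term safety study should not drop a strengthening causal attribution.

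The cost is one sentence and one changed condition in the derivation, with no new data, provided the ratings before and after first dose are in the database; that should be confirmed first. TEAE counts would become slightly lower. Because the change lowers a safety count and the SAP already describes the June 2018 stop of treatment, its reason should be recorded, and the events it removes should be listed.

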13.3. Adverse Events

Adverse events may be volunteered spontaneously by the patient or discovered as a result of general, non-leading questioning. All adverse events should be recorded in the Case Report Form. Adverse events will be collected after signing the informed consent/assent through Visit 18. Information on AEs will be followed to 30 days after the last dose of study drug has been administered.

In the case of withdrawal due to an AE/SAE, the patient will be followed until resolution of the AE, or until in the opinion of the Investigator the event has stabilized, or the investigator does not expect any further improvement or worsening of the subject's condition, and the patient is referred to their primary physician for appropriate management of the ongoing event. Reasonable efforts will be made to contact a patient who fails to attend any follow-up appointments, in order to ensure that he/she is in satisfactory health.

Note: All AEs experienced in SD-005 and medical events occurring between the end of SD-005 and the enrollment into SD-006 after completion of SD-005 should be noted in the medical history for SD-006 at Visit 1 only.

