13.3.2 Assessment of Causality

Severity

The severity (intensity) of each adverse event will be classified by the Investigator as:

Mild: Awareness of sign of symptom, but easily tolerated

Moderate: Sign or symptom causes discomfort, but does not interfere with normal activities

Severe: Sign or symptom of sufficient intensity to interfere with normal activities

Causality

The likely relationship of each adverse event to the medicinal product will be assessed by the Investigator and reported according to the definitions below:

Unrelated:

- Event occurred before dosing or
- Event or intercurrent illness due wholly to factors other than drug treatment.

Possibly

- Reasonable temporal relationship with drug treatment.
- Event could be explained by patient's clinical state or other factors.

Probably

- Reasonable temporal relationship with drug treatment.
- Likely to be known reaction to agent or chemical group, or predicted by known pharmacology.
- Event cannot easily be explained by patient's clinical state or other factors.

Definitely

- Distinct temporal relationship with drug treatment.
- Known reaction to agent or chemical group, or predicted by known pharmacology.

- Event cannot be explained by patient's clinical state or other factors.

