8.7.4.3. Missing Relationship

If the assessment of relationship of the AE to study treatment is missing for any AE, then it will be presented as missing in the listings and in the summary tables.

8.7.5. Summaries of Adverse Incidence Rates for Serious Adverse Events (SAE), Adverse Event Dropouts, and Death

During the treatment period, the number and percentage of patients who experienced TESAEs and separately TEAEs leading to withdrawal from the study will be presented by SOC and by PT within each SOC for each treatment. Treatment-emergent SAEs and separately TEAEs resulting in withdrawal from the study will be similarly presented by severity (mild, moderate, severe), by relationship to study drug (related would include definite, probable, and possible) and by outcome of events. Additionally the number of TESAEs (as opposed to the number and percentage of patients) and separately TEAEs leading to withdrawal will be presented.

Number of patients with TESAEs and separately TEAEs resulting in withdrawal as well as number of TESAEs and separately the number of TEAEs leading to withdrawal will also be presented by the following subgroups of Age (28 days to <2 years, 2 years to <12 years, 12 years to <=18 years, >18 years), EB type and independently. Subgroups for age are defined based at the patient's age at Baseline.

In case that there are non-treatment emergent serious adverse events, they will be listed.

A listing of all serious adverse events and discontinuations due to AEs will be included. Patient with deaths, SAEs or patients who withdraw due to AE will be listed separately and discussed with patient narratives.

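### A carried-over adverse event that stays Severe with unchanged causality can turn serious, prove fatal or cause withdrawal in SD-006 and still be left out of the treatment-emergent incidence tables

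*SAP*

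**What the plan says.** Events from the parent study are assigned to history. Protocol 13.3 states that AEs experienced in SD-005, and medical events in the gap, "should be noted in the medical history for SD-006 at Visit 1 only". SAP 8.7.2 agrees: "Continuing adverse events will also be captured in medical history for the extension study SD-006". It then gives the condition for re-entry: "If the severity or relationship to treatment changed on or after the first dose of study medication, then that AE is considered a TEAE". The new status applies only from the date on which the rating moved.

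The counted tables depend on treatment-emergent status. In SAP 8.7.3, "The number and percentage of patients who experienced TEAEs will be presented by SOC and by PT within SOC for each treatment group", and the breakdowns by severity, relationship and outcome follow the same restriction. SAP 8.7.5 tabulates "the number and percentage of patients who experienced TESAEs and separately TEAEs leading to withdrawal from the study". For serious events without that status it says: "In case that there are non-treatment emergent serious adverse events, they will be listed".

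The severity scale is in Protocol 13.3.2. It has three grades, and the highest reads: "Severe: Sign or symptom of sufficient intensity to interfere with normal activities". Seriousness is defined separately, in Protocol 13.3.1, by outcomes such as death, threat to life and hospitalization.

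**The concern.** Severity and seriousness are different attributes, and the re-entry rule looks only at severity and causality. An event already at the top grade cannot be upgraded when it leads to hospital admission or death. If the investigator sees no reason to alter the causality rating, neither named trigger operates.

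Long-term safety is the primary objective. Every patient arrives from SD-005 with a chronic disease, so events ongoing at entry are to be expected. In the group that received SD-101-6.0 in both studies, such an event may have begun on the same drug. An omission would lower the counts of serious events and of withdrawals due to AEs. It could also leave two tables in disagreement: a patient counted as discontinued for an AE in the disposition summary could be missing from the table of TEAEs leading to withdrawal.

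**Working it through.** The plan gives no figure to reproduce, because the point rests on a definition. The check follows the rule through the tables and then shows the scale.

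**1. Which transitions the rule misses.** The inputs are three severity grades and four relationship categories (Protocol 13.3.2).
- Possible states: 3 × 4 = 12. Before/after pairs: 12 × 12 = 144.
- Pairs with no change in either rating: 12. These leave a carried-over event outside the TEAE set, whatever happens to its seriousness, outcome or action taken.
- If severity does not improve, there are 6 severity pairs × 16 relationship pairs = 96, and the same 12 are missed.
- For an event that starts Severe, no pair has a higher severity. If it stays Severe, only a change in relationship can bring it back.

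These are counts of logical cases, not probabilities.

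**2. Where a missed event appears.** Take a carried-over event that stays Severe with an unchanged relationship, then becomes serious, is fatal or causes withdrawal on SD-006 treatment.

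| Output | Included? |
|---|---|
| TEAE tables, including by outcome (SAP 8.7.3) | No |
| Tables of treatment-emergent serious AEs and TEAEs leading to withdrawal (SAP 8.7.5) | No |
| Separate table of all deaths | None is specified, although the 8.7.5 heading names death |
| Listings of AEs, SAEs and AE discontinuations (SAP 8.7.3, 8.7.5) | Yes |
| Narratives for deaths, SAEs and AE withdrawals (SAP 8.7.5) | Yes |
| Discontinuations by reason (SAP 8.1, 8.7.6) | Yes, if the patient withdrew |

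**3. Scale.** The documents do not say how many patients enter with an ongoing Severe event. SAP 4.4 expects up to approximately 150 patients; I assume 150 treated. The loss per table is (omitted patients) / 150.
- 1 patient: 1/150 = 0.67 percentage points.
- 3 patients: 3/150 = 2.0 points.
- 5 patients: 5/150 = 3.3 points.
- One omitted death: the count would be 0/150 (exact 95% interval 0 to 2.4%) instead of 1/150 (0.02 to 3.7%).

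The tables are also shown by SD-005 treatment group. If the groups were equal in size (a further assumption), one patient would be 1/75 = 1.3 points within a group.

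**The case against.** There are four fair arguments on the other side.

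- **The rule is wider than it first looks.** It refers to a severity that has changed, not worsened. A Severe event that eases to Moderate on SD-006 becomes treatment-emergent, and what follows then counts. A Mild or Moderate event that puts a patient in hospital would normally be regraded to Severe, since it interferes with normal activities. A reader might infer that any carried-over event that turns serious is lost, or that an event Severe at entry can never return. The text supports neither. This argument stands and limits the point to events whose two ratings do not move.
- **Another route may exist.** SAP 8.7.2 says if, not only if. SAP 6.5.2 and Protocol 13.3.1 count exacerbation of a pre-existing condition as a possible AE, and Protocol 13.3.3 requires any SAE to be reported within 24 hours. A site could therefore enter the deterioration as a new SD-006 event. This stands as a possibility. However, neither general definition mentions carried-over events, 8.7.2 deals with them specifically, and the two are not reconciled. The count could depend on how a site chooses to record the event.
- **Nothing disappears from reporting.** This is correct: listings, narratives and the discontinuation summary remain. None of them adds to the numerators in 8.7.3 or 8.7.5.
- **The sentence on listing serious events that are not treatment-emergent may have another target.** It fits events between consent and first dose, which 8.7.2 expressly labels that way. It is therefore not evidence that the authors meant carried-over SAEs only to be listed. It does show that the plan gives no table to an SAE without treatment-emergent status.

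**Conclusion.** The point holds in a narrow form. Under the stated rule, a carried-over event that stays Severe with an unchanged causality rating can become serious, be fatal or lead to withdrawal during SD-006 and be absent from the TEAE, serious-TEAE and TEAE-withdrawal tables. This assumes that the site does not record the deterioration as a new AE, which the documents neither require nor exclude for carried-over events.

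The number of patients affected cannot be derived from the documents. An estimate would need the proportion entering with an ongoing Severe event and the proportion of those events that turn serious or end participation, and neither is given. What can be said is the loss per patient, about 0.7 percentage points on an assumed 150.

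A reader might go further and infer that such events are hidden from the report. The listings, narratives and discontinuation summary rule that out. The defect is in the counted tables for the primary safety objective, and it is cheap to remove.

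**What to change.** - **SAP 8.7.2:** make a carried-over AE treatment-emergent from the date when, on or after the first SD-006 dose, its severity worsens, its relationship to treatment changes, it becomes serious or it results in death. Naming worsening also stops an improvement from creating a TEAE. State which grade worsening is measured against.
- **SAP 6.5.2:** align the general definition with this, and say whether an exacerbation of a carried-over event is a new record or a change to the old one, so that it is counted once.
- **SAP 8.7.5:** also tabulate all SAEs, deaths and AE withdrawals occurring on or after the first SD-006 dose regardless of treatment-emergent status, flagging those ongoing from SD-005. This is better than making withdrawal alone a trigger, because withdrawal would relabel an event whose medical course had not changed.

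The cost is a sentence or two of SAP text, one derivation flag and one extra table. Seriousness, action taken and outcome are already in the AE listing of 8.7.3. SAE and withdrawal counts may be slightly higher.
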